15.5 Analysis of Safety Data and Statistical Monitoring Plan

Interim data analysis for efficacy and futility will not be conducted due to relatively small size and short duration of this clinical trial. Safety data, summarized at the treatment level, will be assessed approximately every 6 months by the DSMB. Adverse Events will be summarized by treatment group and will include incidence by term, severity, relationship to study medication as well as overall incidence rates (regardless of severity and relationship to study medication).

15.6 Sample Size and Power

We are planning to enroll 400 women with VBD, with an estimated attrition rate of 20%. Of note, Reed et al. found that vulvar pain measured on a 0-10 numeric scale has standard deviation 2.0.¹⁰⁴ Salaffi et al¹⁰⁵ noted that 2 points on a 0-10 NRS correspond to a clinically meaningful difference in pain severity. Using these results and assuming the within-subject correlation of 0.5, at a significance level of 0.05, the proposed sample size will provide sufficient power of at least 0.80 to detect differences as small as 0.82 on a 0-10 scale for the overall treatment main effects (3 arms) vs. placebo. To test each individual treatment effect vs. placebo, at a significance level of 0.0167 (Bonferroni-corrected for 3 arms), the proposed sample size can detect differences as small as 0.98 on a 0-10 scale. At a significance level of 0.05, the proposed sample size can detect differences as small as 1.35 and 1.20 on a 0-10 scale for the interaction effect of treatment and each VBD-subtype, given possible splits of 40/60, 50/50, or 60/40 (of note, VBD-p vs VBD-c frequencies were 40/60 at UNC and 50/50 at UCLA clinics in previous studies).

To calculate power for research question IIIa, we used data from our previous study of biomarkers in VBD patients.⁷ Conservatively assuming that VBD-c patients represent 60% (192/320) of the sample and VBD-p patients represent 40% (128/320) of the sample, and adjusting the significance threshold for 4 tier 1 cytokine tests, we will be able to detect mean differences of at least 0.4 SD with the power of 0.84 or greater using a t-test. For IL-8, 0.4 SD translates to approximately 2 pg/mL, and for IL-1ra 0.4 SD translates to 240 pg/mL of the minimal detectable difference. Of note, the mean differences between controls and VBD patients for IL-8 and IL-1ra in our previous study were 4 pg/mL and 300 pg/mL, respectively. Thus, we have sufficient power to detect plausible differences in cytokine levels between the VBD subgroups.

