15 STATISTICAL CONSIDERATIONS

15.1 VBD Subtype Designation

Women with VBD-c will be distinguished from those with VBD-p based on the presence of a COPC. The Institute of Medicine's 2011 report, *Relieving Pain in America*, identified 9 COPCs that predominantly affect women and frequently co-occur with VBD.⁹³ The presence of a COPC will be determined using the COPC survey. This is an easy-to-complete form including modules with check-box questions and a body mannequin to determine the presence of 9 COPCs: 1) FMS, 2) TMD, 3) back pain, 4) IBS, 5) chronic tension-type headache, 6) chronic migraine, and 7) chronic fatigue syndrome, 8) endometriosis, and 9) interstitial cystitis. Women with VBD and no COPCs will be designated as VBD-p, while women with VBD and ≥ 1 COPC will be designated as VBD-c. These criteria will be used as a primary method to distinguish between VBD-p and VBD-c in this study.

We, however, acknowledge that the criteria to distinguish VBD subtypes needs further exploration. In particular, it is possible that the optimal cutoff for VBD-c requires more than one COPC to be present. Therefore, as a secondary method to characterize VBD subtypes, we will calculate a continuous COPC 'centralness' score defined as the number of COPCs present ranging from 0 to 9. This continuous COPC score will be used to identify the optimal cutoff value between VBD-p and VBD-c in terms of treatment response.

To further characterize the two VBD subtypes, we will also measure generalized pain at 'neutral' non-pelvic sites using a quantitative sensory testing approach designed by [name] and colleagues.^{94, 95} The 3 neutral sites (deltoid muscle, shin, trapezius) are remote from the pelvic region and not used for diagnosing other pain conditions, but reflect an individual's overall

pressure pain sensitivity.⁹⁸⁻¹⁰⁰ An algometer will be applied to the 3 sites, with continuously ascending pressure at a rate of 1 kg/s to a maximum of 10 kg. Participants will indicate when the evoked sensation first becomes painful. A composite pressure pain threshold (PPT) score will be compared between VBD-c and VBD-p subgroups using ANCOVA. We would expect women with VBD-p to have higher PPT scores (less pain) and women with VBD-c to have lower scores (more pain) at these sites.

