15.4 Analysis of the Aim 3 Endpoints

Cytokine Expression levels will be measured in vaginal lavage samples and plasma isolated from whole blood. We will use a standard Human MesoScale Discovery multiplex kit to measure 36 inflammatory mediators (4 tier-1 and 32 tier-2).

Tier-1 mediators include the pro-inflammatory cytokines IL-1 β ,⁵⁹⁻⁶¹ IL-8,^{7,60,62} and IL-17⁶³ and anti-inflammatory cytokine IL-1ra.^{7,61} These cytokines were selected based on previous associations with VBD case status and symptom severity.

Tier-2 mediators include cytokines (e.g., interleukin 6; IL-6), chemokines (e.g., monocyte chemoattractant protein 1; MCP1), and growth factors (e.g., vascular endothelial growth factor; VEGF) that are involved in peripheral and central sensitization, inflammation, and chronic pain.¹²⁸

miRNA Expression levels will be measured in vaginal swab samples and blood. We will isolate total RNA and then ship the RNA to UT Health Genome Sequencing Facility (GSF), directed by [name]. The GSF core will perform small RNA library preparation and sequencing.

Data Analysis. The two primary statistical questions for Aim 3 are: 3a) At baseline, is there an inverse association between VBD 'centralness' score (determined by the number of COPC sites) and the levels of Tier-1 cytokines in vaginal samples; and a positive association between VBD 'centralness' score and the levels of Tier-1 cytokines in plasma samples? 3b) Do biomarkers in vaginal fluid predict response to peripheral treatment and biomarkers in blood predict response to central treatment?

To answer question 3a, we will fit a linear regression model where cytokine level (skewed variables will be transformed (e.g., log, box-cox) to approximate normal distribution) will be a continuous dependent variable and VBD 'centralness' score, will be the main predictor of interest. Covariates will include age and race. Significance of regression coefficient associated with the 'centralness' score will be evaluated using an F-test and significance threshold (alpha) Bonferroni-corrected for the number of cytokines assessed (4 cytokines corresponding to 4 statistical tests). Subgroup means, mean differences and 95% confidence intervals will be output.

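### The 0.84 power stated for question 3a belongs to a VBD-c versus VBD-p t-test, not to the planned regression slope on the COPC count, whose power is not given

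*Combined protocol and SAP*

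**What the plan says.** Section 15.4 poses question 3a as an association, at baseline, between the centralness score and the Tier-1 cytokines, inverse in vaginal samples and positive in plasma. In the linear regression, the "VBD 'centralness' score, will be the main predictor of interest", with age and race as covariates. The test is explicit: "Significance of regression coefficient associated with the 'centralness' score will be evaluated using an F-test", with alpha Bonferroni-corrected for four cytokines. The paragraph ends: "Subgroup means, mean differences and 95% confidence intervals will be output".

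Section 15.1 defines the score as a COPC count, "defined as the number of COPCs present ranging from 0 to 9". It also sets a binary rule: "Women with VBD and no COPCs will be designated as VBD-p", and women with at least one COPC are VBD-c. Of the binary rule it says: "These criteria will be used as a primary method to distinguish between VBD-p and VBD-c in this study". The count is introduced as a secondary method.

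Section 15.6 gives power for this question (written there as IIIa) with 192 VBD-c and 128 VBD-p women and alpha adjusted for four tests: "we will be able to detect mean differences of at least 0.4 SD with the power of 0.84 or greater using a t-test". It concludes that power is sufficient for differences between the VBD subgroups. It gives no power for a slope on the count.

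**The concern.** The powered test and the planned test use different predictors. The t-test compares none with any COPC. The regression asks whether the cytokine level changes with each additional COPC. For the same 0.4 SD subtype difference, power can differ widely between them, depending on how the counts are spread among VBD-c women and on how the cytokine level depends on the count.

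Two things are at stake. A reader of Section 15.6 would take 0.84 as the chance that the 3a test succeeds, and nothing in the plan supports that. Also, Section 15.4 promises subgroup mean differences, but the only model it describes has a coefficient per COPC. An analyst could then have two candidate results for 3a, a slope and a subtype contrast, with no written rule for which one answers the question.

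**Working it through.** **Inputs from the documents.** Total 320 (400 enrolled, 20% attrition); 60% VBD-c and 40% VBD-p; subtype difference 0.4 SD; alpha 0.05/4 = 0.0125; count 0 to 9, with VBD-p at 0. Sidedness is not stated; two-sided is assumed.

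**Step 1: the plan's figure.** Noncentrality = 0.4 × √(320 × 0.4 × 0.6) = 3.505 on 318 df. Power is 0.839 by the exact noncentral t and 0.843 by the normal approximation. The stated 0.84 is right for the t-test.

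**Step 2: power of the slope.** Let x be the count and g(x) the mean cytokine shift in SD units, with g(0) = 0, a mean of g among VBD-c women of 0.4, and residual SD 1. Then

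- ρ = Cov(x, g) / √[Var(x) × (Var(g) + 1)]
- λ = 320 × ρ² / (1 − ρ²)
- power = P[F(1, 318; λ) exceeds the upper 0.0125 point of F(1, 318)].

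Covariates are left out, as in the plan's own t-test. If every VBD-c woman has one COPC, ρ = 0.4 × √0.24 / √(1 + 0.16 × 0.24) = 0.192 and power is 0.839, the t-test value. The same holds for any count shared by all VBD-c women. Otherwise the tests differ.

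**Step 3: two worked cases, counts uniform on 1 to 9 among VBD-c.** The mean among VBD-c is 5, and Var(x) = 10.0 over the whole sample.

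- Step at one COPC: the correlation r of count with subtype is 0.24 × 5 / √(0.24 × 10.0) = 0.775. So ρ = 0.192 × 0.775 = 0.149, λ = 7.27, power 0.57.
- Linear: the slope is 0.4/5 = 0.08, so λ = 320 × 0.08² × 10.0 = 20.5, power 0.98.

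**Step 4: range.** The documents give no count distribution, so those below are assumptions. Each has 40% of women at zero. The last four columns are slope power at N = 320.

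| Counts among VBD-c | r with subtype | Step at 1 | Square root of count | Linear | Step at 2 |
|---|---|---|---|---|---|
| 80% one, 20% two | 0.89 | 0.72 | 0.84 | 0.93 | 1.00 |
| 60/25/10/5% at 1/2/3/4 | 0.76 | 0.56 | 0.85 | 0.98 | 1.00 |
| Geometric, ratio 0.5 | 0.68 | 0.44 | 0.87 | 0.996 | 0.996 |
| Geometric, ratio 0.7 | 0.67 | 0.43 | 0.89 | 0.996 | 0.94 |
| Uniform 1 to 5 | 0.80 | 0.61 | 0.87 | 0.97 | 0.93 |
| Uniform 1 to 9 | 0.77 | 0.57 | 0.89 | 0.98 | 0.80 |

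Holding the subtype difference at 0.4 SD makes some cells extreme. In the first row, a step at two needs a shift of 0.4/0.2 = 2 SD in the women with two COPCs.

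**Step 5: a figure that needs no count distribution.** Setting power to 0.84 at N = 320 and alpha 0.0125 and solving for ρ gives a correlation of about 0.19 between count and cytokine level.

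**The case against.** The best defence is that Section 15.4 is consistent within itself on the test: the question, the predictor and the F-test all concern the score. Section 15.1 ranks the binary rule first for telling the subtypes apart, but does not require every model to use it. It also allows that the best cutoff may be more than one COPC, which is a reason to prefer the count. A two-group t-test is then a rough stand-in for a regression. Most of this stands, and it confines the clear conflict to the power paragraph. The stand-in argument does not. It works when the predictor is the group indicator, but here the correlation between predictor and indicator is 0.67 to 0.89 in the assumed cases.

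A reader might infer more than the documents support, in three ways.

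- *That 3a is underpowered.* This follows only if the effect is a step at exactly one COPC. No section hypothesises such a step. Section 4 links higher levels to a subtype, which a gradient also satisfies. For the other shapes tried, slope power is about 0.80 or higher.
- *That the trial will not report the subtype difference.* Section 15.4 plans to output subgroup means and differences; it leaves out the model for them.
- *That the binary contrast must become the primary test.* That is a trade-off. If the true step is at two COPCs, the same formula with the binary indicator in place of x gives power of 0.68 to 0.83 over the six distributions.

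**Conclusion.** The point holds as a mismatch between the powered test and the planned test. The 0.84 is correct for the binary comparison and is not the power of the 3a slope test. The power of that test is unknown and could fall on either side of 0.84: about 0.43 to 0.72 for a step at one COPC, and about 0.80 to above 0.99 for the graded shapes and the step at two.

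The mismatch itself rests on the text alone. The ranges rest on assumed count distributions and effect shapes, a two-sided alpha of 0.0125, no covariates, and the plan's own N of 320, although 3a is a baseline analysis and attrition may not apply to it. The reach is limited: 3a is a baseline biomarker association, Section 15.6 does not derive the 400 from it, and no treatment comparison changes.

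**What to change.** In Section 15.6, replace the 0.84 with the power of the planned slope test under a stated COPC-count distribution and effect shape, or with its minimum detectable correlation (about 0.19 for power 0.84 at N = 320). If the 0.84 is kept, label it as applying only to the binary VBD-c versus VBD-p comparison.

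In Section 15.4, state that the subgroup means, differences and intervals come from a separate binary-subtype model with the same covariates. Pre-specify which of the two tests is primary for 3a.

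The cost is wording only. The COPC inventory and the baseline blood and vaginal samples are already scheduled, so nothing new is measured. The downside is that one reassuring power figure becomes a range that may be less favourable.

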16 DATA MANAGEMENT PROCEDURES

16.1 Overview of Data Management

The CC will have primary responsibility for data management, including the development of data collection systems, data monitoring processes, and data storage and back-up. State-of-the-art technology will be used for the management of the network's data.

eCRF: The CC team will develop modules, designed in Redcap, that will capture patient responses to questions having to do with their VBD symptoms. The Redcap instruments will include an enrollment and demographics form; forms for recording relevant history, Pain symptoms, vulvar exam results, laboratory results, baseline biomarker levels, and other baseline presenting characteristics; follow-up forms for use during regular follow-up visits; forms to track the participant's clinical course over time; and others that track all related information for Patients that meet the trial criteria.

System: The data will be collected in a validated, IRB approved Redcap survey environment. The CC team of skilled data managers and programmers will design and produce a tailored network system that provides operational efficiency and meaningful reporting of metrics.

Data Management Process: The Redcap survey environment will be used for data entry and simple reports. All data will be entered into Redcap by personnel at the clinical sites. Any out-of-range values and missing key variables will be flagged and addressed in real-time at the site during data entry. When a query is generated on a particular variable, a flag is raised in a database field; the system tracks the queries and produces reports of outstanding queries. Queries can also be generated from manual or statistical review of the data forms.

The CC will create reports to identify trends in the data that may require additional clarification and training. These reports will be available to the sites and to the study leadership as we work with the sites to correct negative trends and eliminate future data errors. The CC will perform internal database quality-control checks during the study to identify systematic deviations requiring corrections.

Data Quality Control: A three-step approach to data quality control will be implemented.

1. Training: Prior to the start of enrollment, the Investigators and Nurse Practitioners will be trained on the clinical protocol and data collection procedures. Recent site surveys indicate that most Coordinators are very familiar with the EDC system, so training is typically targeted to a specific protocol. For Coordinators new to REDCap, the CC will provide training with hands-on database interaction, demonstration of key REDCap system functionality, and practice exercises. Personnel at the clinical sites will enter the data mandated by the protocol into REDCap. All CRFs will be completed according to the current Good Clinical Practice (GCP) guidelines. The CC will conduct follow-up training and training for new study personnel as needed.
2. Monitoring: A CC monitor will visit sites during the enrollment period to ensure that data collection is being handled properly, to provide in-service training, and to address questions from site investigators and coordinators. Additional details will be outlined in the Clinical Monitoring Plan.
3. Managing data: A series of computerized data validation checks will be programmed by the CC to check for missing data, inconsistencies in the data or data that is out of range. After the data have been exported from the EDC system to SAS for statistical summarization and data analysis, further cross-checking of the data will be performed by the CC and queries issued through REDCap for any discrepancies.

16.2 Data Security

Access to databases will be controlled centrally by the CC through user passwords linked to appropriate privileges. This protects the data from unauthorized changes and inadvertent loss or damage. Database and web servers will be secured by a firewall and through controlled physical access. Database back-up will be performed daily using standard procedures in place at the CC. All disk drives that provide network services, and all user computers, will be protected using virus-scanning software.

16.3 Publication Policy

Dissemination of preliminary information can adversely affect the objectivity of study data. For this reason, Investigators will be prohibited from performing subset analyses at any point prior to the conclusion of the study, and any data, other than safety data, cannot be used for publication or reporting outside of this study until the study is completed or discontinued by the DSMB or NICHD.

17 STUDY ADMINISTRATION

17.1 Data and Safety Monitoring Board

As noted above, the DSMB will be composed of 4 members: a physician, a statistician, a patient representative, and a bioethicist. All DSMB operations will be managed by the DCRI.

DSMB Charter and Meetings. The DCRI Statistical Team will develop a DSMB Charter that details specific data tables to be provided and procedures to be followed. The DSMB Charter will also describe the overall mission, responsibilities, and meeting schedule of the board. The DCRI statistical team will be responsible for DSMB charter review and approval. The draft charter will be submitted for review and approval by NICHD, the DSMB chairperson, and study Investigators prior to study enrollment. After the charter has been finalized, any changes to the plan will be documented in the minutes of the DSMB meeting. At the conclusion of each DSMB meeting, the DSMB Chair will make a recommendation to the study team about continuation of the trial. It is expected that the DSMB will meet every 6-months. If safety issues arise, additional conference calls can be requested by the DSMB chairman. DCRI statistical team will coordinate and convene all DSMB meetings.

17.2 Coordinating Center

[name] will function as the Clinical CC, [name] will function as the Data Management CC, and the DCRI will function as the Statistical CC for this trial.

17.3 Core Laboratories

17.3.1 Central Compounding Pharmacy and Pacifica Compounding Pharmacy

The investigational product (IP) and placebo capsules to be dispensed at UNC will be prepared by Central Compounding Pharmacy, directed by [name], and shipped to study personnel at the UNC Hillsborough clinic.

The IP and placebo capsules to be dispensed at UCLA will be prepared by Pacifica Pharmacy, directed by [name].

17.3.2 Substrate Services Core

The Substrate Services Core, directed by [name], will provide quality control and a state-of-the-art repository for study samples. Precise sample inventory will be facilitated through a 2D Barcode system. This system includes the sample tubes themselves, which have a 2D barcode with 14-digit alpha-numeric code etched on the bottom of the sample tubes. A scanner will be used to ensure accurate reading of barcodes, and the data will be downloaded into the LabVantage Laboratory Information Management System (LIMS) for electronic inventory.

17.3.3 Sequencing Core

Isolated RNA will be shipped from the Substrate Services Core to the University of Texas Health Genome Sequencing Facility (GSF), directed by [name]. The GSF core will perform small RNA library preparation and sequencing.

18 ETHICAL AND REGULATORY CONSIDERATIONS

18.1 Ethics and Good Clinical Practice

This study must be carried out in compliance with the protocol to ensure adherence to Good Clinical Practice, as described in the following documents:

1. ICH Harmonized Tripartite Guidelines for Good Clinical Practice 1996.
2. US 21 Code of Federal Regulations dealing with clinical studies (including parts 50 and 56 concerning informed consent and IRB regulations).
3. Declaration of Helsinki, concerning medical research in humans (Recommendations Guiding Physicians in Biomedical Research Involving Human Subjects, Helsinki 1964, amended Tokyo 1975, Venice 1983, Hong Kong 1989, Somerset West 1996).

By signing the protocol, the investigator agrees to adhere to the instructions and procedures described in it and thereby to adhere to the principles of Good Clinical Practice to which it conforms.

18.2 Institutional Review Board

Before implementing this study, the protocol, the proposed informed consent form and other information available to subjects, must be reviewed by a properly constituted Institutional Review Board (IRB). A signed and dated statement that the protocol and informed consent have been approved by the IRB must be provided to the CC before study initiation. Any amendments to the protocol, other than administrative ones, must be approved by this committee.

18.3 Informed Consent Procedures

18.3.1 Informed Consent

The Investigator or designee must explain to each subject (or legally authorized representative) the nature of the study, its purpose, the procedures involved, the expected duration, the potential risks and benefits involved and any discomfort it may entail. Each subject must be informed that participation in the study is voluntary and that he/she may withdraw from the study at any time and that withdrawal of consent will not affect his/her subsequent medical treatment or relationship with the treating physician.

This informed consent should be given by means of a standard non-technical language. If a patient agrees to participate in the Vestibulodynia: Update study, they will review and sign the IRB-approved electronic Informed Consent Form (eICF). No patient can enter the study before her informed consent has been obtained.

